1.1 Functions of the Data and Safety Monitoring Board

The DSMB will function as an independent body charged with monitoring the safety of study participants, and ensuring that the scientific goals of the study are met. To support these goals, the DSMB will review data and safety monitoring reports.

1.2 Monitoring of Safety Data by the DSMB and the Research Team

Range of Safety Reporting by the study team to the DSMB. The study team will provide the following information to the DSMB for its review on an annual basis: Serious Adverse Events (SAEs), Unanticipated Adverse Events (UAEs), Adverse Events (AEs), Unanticipated Problems (UPs), study retention rates, reasons for early study withdrawal, and abnormal laboratory values that are determined to be related to study participation. The DSMB will have access to any additional data it deems necessary to fulfill its mission. The study team will respond promptly to any DSMB data requests.

Anticipated Adverse Events

Anticipated Adverse Events for this study include the following:

- Emotional upset due to questions during the assessment about participants’ psychiatric and social histories (including current suicidal ideation, history of suicide attempts, and history of physical or sexual abuse);
- Pain, swelling or infection due to phlebotomy for blood laboratory testing;

- Nausea, diarrhea, vomiting, abdominal gas or bloating, appetite changes, headache, edema or weight gain associated with administration of the investigational drug creatine;
- Injury due to mobilization of metallic objects inadvertently brought or worn by the participant into the MRI scanner. (The MRI technicians will make every effort to avoid this by reminding the participant and their parent or guardian to take the appropriate precautions prior to entering the scanning suite. An MRI safety questionnaire must be completed by participants immediately prior to each scanning session.);
- Claustrophobia (fear of being in small spaces), dizziness, headache, metallic taste in the mouth, double vision, visions of flashing lights, or tingling in the back during the MRI scans. All of these events are rare, temporary and not medically dangerous.
- Worsening depression, suicidal ideation, and/or suicide attempts as part of the illness of MDD.

The effects of creatine and MRI scans on a developing fetus are unknown, so participants will undergo pregnancy testing, and will be withdrawn from the study if they have a positive pregnancy test. Sexually active persons unwilling to practice contraception during the study will be excluded from participation.

Unanticipated Adverse Events are defined as events associated with study participation not listed above. All SAEs will be reported to the FDA, regardless of whether they are “anticipated” or “unanticipated.”

Other Safety-Related Reports – The DSMB will also receive an annual summary report of treatment retention and reasons for withdrawal.

Reporting of Letters or Notices Issued by the FDA – In accordance with NIH Notice OD-00-053 and the applicable Federal law [45 CFR 74.51 (f)], the principal investigator will report to the NIMH (the grant awarding agency) any communication from the FDA regarding the safety of the investigational drug, within 72 hours of receiving it. Immediate notification will be made by telephone, and a copy of the FDA correspondence will be faxed and mailed to the NIMH. The FDA communications covered by 45 CFR 74.51 (f) include the following: Warning Letters, Notice of Initiation of Disqualification Proceedings and Opportunity to Explain Letter (NIDPOE), Notice of Opportunity for Hearing (NOOH), Notice of Disqualification, Consent Agreements, and Clinical Hold Letters. Simultaneous transmission will be made locally to the IRB.

The study will adopt the following **Stopping Rules**:

- At any time during the study, if the DSMB unanimously agrees that the risks to participants outweigh the potential benefits, the DSMB will recommend to the IRB and the principal investigator that the study be stopped. The DSMB chairman will communicate this to the IRB and the principal investigator.
- If a unanimous recommendation to stop the study is made by the DSMB, the study will be halted. Recruitment will be closed, and the study team will contact all active and inactive study participants. The FDA, NIMH, and investigational drug manufacturer will also be notified.
- If the study is stopped, active study participants will be instructed to discontinue the investigational drug, and follow-up safety visits will be scheduled for all participants.

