- The principal investigator retains the right to withdraw participants from the study without their permission, in the event they are unwilling or unable to maintain adherence to the research protocol.

HEALTHY COMPARISON SUBJECTS

Inclusion Criteria:

- Participants must be able to grant informed consent (age >18), or parent/guardian permission plus participant assent (age <18).
- Participants must be female.
- Participants must be between the ages of 12 and 21 years.
- Participants must not meet DSM-IV-TR criteria for a current psychiatric illness or substance use disorder.
- Participants must have a CDRS-R score ≤ 30 .

Exclusion Criteria:

- Unstable medical or neurological illness.
- Clinically significant psychiatric or substance use disorder.
- Pregnant subjects, due to the unknown effects of MRI/MRS scans on a fetus. In addition, women of childbearing potential who are unable or unwilling to practice contraception during the study will be excluded. Female participants who are of childbearing potential must have a negative urine pregnancy test before the MRI/MRS scan.
- Participants with a contraindication to MRI/MRS scanning, such as a metallic implant.

Study Withdrawal Criteria:

- Withdrawal of parental permission or participant assent.
- Onset of a psychotic disorder or depression.
- Positive pregnancy test.
- A significant change to the participant's medication or psychotherapy treatment from the regimen reported at their baseline/screening visit, unless directed by the principal investigator.

DESIGN:

The proposed study will use a randomized double-blind placebo-controlled design. Sixty-six participants will be randomly assigned in a 1:1 ratio to placebo or 10g of oral daily creatine monohydrate augmentation for eight weeks.

The study's design is consistent with the acceptable ethical justifications for the use of placebo controls outlined in the University of Utah Institutional Review Board's (IRB's) Investigator Guidance on Placebo Comparators (Version B0608). Specifically, this study fits situations #3, #4 and #5 of the Guidance:

- "*Participants are refractory to the available therapies by virtue of their past treatment history*" (#3): by definition, the proposed study will recruit female adolescents with SSRI-resistant a.k.a. treatment-refractory depression. To meet the study's inclusion criteria, participants must have failed an adequate trial of the standard-of-care intervention.

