- The brain scans may improve our understanding of the biology of depression in female adolescents. However, that would not directly benefit the participants.
- The participants will receive a copy of the clinical MRI of their brain, if they wish. A copy of the MRI scan report will also go to the research team.

DATA SAFETY AND MONITORING:

The principal investigator and study coordinator will perform monitoring of the study records on a continuous basis. Unanticipated problems and adverse events that are related to the research, or which place participants at greater-than-expected risk, will be reported to the IRB within 10 working days of learning of the event.

Unanticipated problems involving risk to participants or others are defined as any incident, experience or outcome that meets the following criteria:

- Unforeseen (not expected by the researcher or the research participant) given the research procedures and the subject population being studied;
- Related or probably related to participation in the research, or if the event or problem probably or definitely affects the safety, rights and welfare of current participants; and
- Suggests that the research places participants or others at a greater risk of harm (includes physical, psychological, economic or social harm) than was previously known or recognized.

An *unexpected adverse event* is any adverse event occurring in one or more subjects participating in a research protocol, whose nature, severity, or frequency is not consistent with either:

- The known or foreseeable risk of adverse events associated with the procedures involved in the research that are described in the protocol related-documents (i.e. protocol, investigational brochure, consent form, or product labeling).
- The expected natural progression of any underlying disease, illness or medical condition of the subject experiencing the adverse event.

[name] will make the initial determination if an unexpected, adverse event is related or unrelated to the investigational drug or a clinical or research study procedure. An adverse event is “related to the research” if in the opinion of the principal investigator or co-investigator, it was more likely than not related to the investigational agent or intervention.

Study Premature Termination / Withdrawal Criteria:

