- 2) *Telephone and facsimile transmission safety reports.* The principal investigator shall also notify FDA by telephone or by facsimile transmission of any unexpected fatal or life-threatening experience associated with the use of the drug as soon as possible but in no event later than 7 calendar days after the event. Each telephone call or facsimile transmission to FDA shall be transmitted to the FDA new drug review division in the Center for Drug Evaluation and Research or the product review division in the Center for Biologics Evaluation and Research that has responsibility

for review of the IND.

3) *Reporting format or frequency.* FDA may request that the principal investigator submit IND safety reports in a format or at a frequency different than that required under this paragraph.

d) Follow-Up:

- 1) The research team shall promptly investigate all safety information received by it.
- 2) Follow-up information to a safety report shall be submitted as soon as the relevant information is available.
- 3) If the results of the team's investigation show that an adverse drug experience not initially determined to be reportable is so reportable, the researchers shall report such experience in a written safety report as soon as possible, but in no event later than 15 calendar days after the determination is made.
- 4) Results of the team's investigation of other safety information shall be submitted, as appropriate, in an information amendment or annual report to the FDA.

Reporting to the University of Utah Institutional Review Board (IRB)

The study team will strictly observe the University of Utah IRB policy that requires researchers to submit reports of events that may represent unanticipated problems (UPs) involving risks to participants and others, including unexpected, research-related adverse events. Reports will be submitted to the IRB as soon as possible after the principal investigator learns of the event, but in all cases within 10 working days. Late reports will be accompanied by a written explanation from the principal investigator as to why the report is tardy.

The following will be reported promptly by the principal investigator to the IRB:

- Unexpected, research-related adverse events;
- Breached of confidentiality or privacy that involves real or potential risk such as unauthorized use or disclosure of protected health information (PHI);
- New information indicating a change to the risks or benefits of the research, such as:

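### In the text available, serious adverse events reach the DSMB only in an annual package and routine laboratory reports are filtered by relatedness, although its stopping rule is meant to work at any time

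*Combined protocol and SAP*

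**What the plan says.** Section 1.2 sets the routine flow of safety data: "The study team will provide the following information to the DSMB for its review on an annual basis". The list that follows includes SAEs, unanticipated adverse events, all other adverse events, unanticipated problems, retention and reasons for withdrawal. None of those event categories is limited by relatedness. The laboratory item is: it covers "abnormal laboratory values that are determined to be related to study participation". The same paragraph adds that "The DSMB will have access to any additional data it deems necessary to fulfill its mission" and requires the team to answer such requests promptly.

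The stopping rules, also in section 1.2, open with "At any time during the study, if the DSMB unanimously agrees that the risks to participants outweigh the potential benefits". They give no numerical trigger. Section 1.3 ties the DSMB's letter recommending continuation or a halt to its review of an annual report.

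Other bodies have clocks. For the IRB, "Reports will be submitted to the IRB as soon as possible after the principal investigator learns of the event", with an outer limit of 10 working days. The FDA section sets 7 and 15 calendar days for defined classes of event. Section 1.2 also says that every SAE goes to the FDA, anticipated or not, but gives no time limit for that.

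**The concern.** A rule that can be used at any time needs information that arrives at any time. As written, the body holding the rule is told of SAEs once a year, while the IRB and the FDA hear of some of them within days or weeks. The population is depressed adolescents on an SSRI, and section 1.2 itself lists suicidal ideation and attempts among the anticipated events. Whether such events are more frequent on one arm is a question for an independent body that can compare arms. A single investigator's view of a single case cannot answer it.

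The laboratory filter raises the same issue. The Data Safety and Monitoring section treats an adverse event as related if, in an investigator's opinion, "it was more likely than not related to the investigational agent or intervention". If laboratory values are judged in the same way by staff who are blinded in the 8-week phase, values that look unremarkable one at a time could be left out even when they are more common on one arm. The protocol treats renal safety as relevant: it excludes pre-existing renal disease and baseline proteinuria.

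**Working it through.** The plan states no figure for this point, so there is none to reproduce. The check compares intervals and reporting routes.

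**Inputs**
- Interval between DSMB safety reports: 1 year, 365.25 days (section 1.2).
- Blinded exposure: participants are "randomly assigned in a 1:1 ratio to placebo or 10g of oral daily creatine monohydrate augmentation for eight weeks" (Design), so 8 × 7 = 56 days.
- Open-label exposure: optional, 6 months (Design), 365.25 / 2 = 182.6 days.
- Randomised: 66. Award: 3 years (background section on creatine in females). The protocol gives no accrual rate.

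**Exposure against the interval**
- Total: 56 + 182.6 = 238.6, about 239 days, which is less than 365.25.
- Longer reading, 10 weeks + 7 months: about 283 days, also less than 365.25.

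**Share of participants whose exposure falls wholly between two reports**, if start dates are uniform over the year (assumption): (365.25 − exposure) / 365.25.
- Blinded phase: (365.25 − 56) / 365.25 = 0.847, about 85%.
- Blinded phase plus full extension: (365.25 − 238.6) / 365.25 = 0.347, about 35%. On the longer reading, (365.25 − 283.1) / 365.25 = 0.225, about 22%.

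**Wait before the DSMB sees an SAE**, absent a request: at most 365 days; on average 365.25 / 2, about 183 days, if events are uniform over the interval.

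**Participants randomised during that wait**
- Even accrual over 3 years (assumption): 66 / 3 = 22 per year, so up to 22 and on average 22 / 2 = 11. With 1:1 allocation about half of these receive creatine in the blinded phase.
- Even accrual over 2 years, to show the range: 66 / 2 = 33 at most, 16.5 on average.

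**Reporting routes side by side**

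| Recipient | Events covered | Clock |
|---|---|---|
| FDA, telephone or fax | Unexpected, fatal or life-threatening, drug-associated | 7 calendar days |
| FDA, written | Serious, unexpected, drug-associated | 15 calendar days |
| FDA, section 1.2 | All SAEs | None stated |
| IRB | Mainly unanticipated problems, and adverse events that are research-related or raise risk above what was expected | 10 working days |
| DSMB | All SAEs, other adverse events, unanticipated problems | Annual |

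Now take a suicide attempt that meets the SAE definition and is judged part of the illness. It is on the anticipated list and is not attributed to the drug, so neither FDA clock starts. It is not unexpected and research-related, so the IRB clock need not start unless someone judges that it shows greater-than-expected risk. It goes to the FDA with no deadline, and to the DSMB in the annual package.

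**The case against.** The strongest objection is that the visible text is incomplete. The plan's list of components promises a review process and a meeting schedule, and the part between that list and section 1.1 was not available. It could contain an event-driven route, and section 1.2 does not say that the annual package is the only one. This stands, and the point is limited accordingly. A meeting schedule alone would not close the gap, because section 1.2 expressly places SAEs in the annual flow.

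Three stronger readings are tempting, and the documents do not support them.

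- *A reader might infer that the DSMB is unable to act between reports.* It may ask for any data and must be answered promptly, and it could make a standing request for every SAE. The weakness is that the plan relies on the DSMB's initiative and states nothing that would tell it to ask.
- *A reader might infer that the laboratory filter prevents a comparison between arms.* It applies only to the laboratory item. An abnormal value recorded as an adverse event still appears in the annual listing, and full laboratory data can be requested. Nor does section 1.2 say who decides laboratory relatedness; that blinded staff do so is an inference. The filter weakens the comparison.
- *A reader might infer that participants go unmonitored for a year.* The investigator reviews records continuously, suicidality and adverse events are assessed at scheduled visits, individual withdrawal criteria apply, and the FDA and IRB receive reports. The gap concerns the DSMB.

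The size also needs care. Twenty-two is the worst case under even 3-year accrual. The 239 days apply only to those who take the full extension. The extension has no placebo arm, so a concurrent comparison exists only in the 8-week phase.

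**Conclusion.** The concern holds in this limited form. In the text available, SAEs and unanticipated problems have no expedited route to the DSMB, the routine laboratory item is restricted by a relatedness judgement, and the stopping rule presumes more timely information than the plan supplies.

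That total exposure is shorter than the reporting interval follows from the protocol's own durations. The possible one-year wait assumes that the DSMB makes no request and that the unavailable text adds no faster route. The 85% and 22–35% shares assume uniform start dates; the 22 (11 on average) assumes even accrual over 3 years.

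The most consequential part is the handling of anticipated events. The harm most expected in this population is the one least well covered by the existing clocks. The DSMB could, rather than necessarily would, learn of an imbalance only after many participants had finished blinded treatment. This should be corrected; it does not affect the planned efficacy analysis.

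**What to change.** In section 1.2, require every SAE, anticipated or not and related or not, and every unanticipated problem to be sent to the DSMB within a stated deadline of its own. The 10 working days already used for the IRB would serve as an example. Copying the DSMB on reports made to the IRB or FDA would not be enough, because an anticipated SAE may have no timed report to copy. Keep the annual report for aggregate data.

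Replace the laboratory item with a listing of all abnormal post-baseline values by coded arm, showing the relatedness judgement as a column and not using it as a filter. If the monitoring plan already contains an event-driven route elsewhere, cross-refer to it in section 1.2.

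The change is to monitoring-plan wording only. Visits, treatment and sample size are unaffected. Post-baseline laboratory tests are scheduled only at week 8 and month 6 (Tables 1 and 2), apart from discretionary extras, so the listing is short. The cost is slightly more DSMB correspondence and a brief report for anticipated SAEs that at present have no timed report.
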